1.2. Schema

Figure 1: Schematic Overview of Study VAC31518COV3009

Active Ad26.COV2.S; incl. including; LTFU long term follow up; rand. randomization; Th T helper cell type 1/2.

^a Available safety data from all ongoing studies with Ad26.COV2.S will be taken into account.

A screening phase of up to 28 days is included, however, screening may also be performed prior to randomization on the day of vaccination.

The enrollment for Stage 1 and Stage 2 will be staggered. In both stages, participants will be enrolled in 1 of the 2 age dependent subgroups (≥ 18 years to < 60 years of age or ≥ 60 years of age). Once Stage 2 is initiated, participants with and without relevant comorbidities can be recruited. It is intended that a minimum of approximately 30% of recruited participants will be ≥ 60 years of age and approximately 20% of recruited participants will be ≥ 18 to < 40 years of age. The analysis of the data will not be staggered: the primary analysis will be based on pooled data from both stages of the study.

Refer to Section 2.1 for details on initiation of study VAC31518COV3009 based on data from study VAC31518COV1001.

Refer to the Investigator's Brochure (IB) for details about the VAC31518COV1001 study.^{40,41}

Refer to Section 5.2 for details on the relevant comorbidities.

Note: Upon implementation of Amendment 4, all participants from double blind phase will be unblinded and the study will continue as an open label study. Participants who received either one dose or two doses of placebo at that time will be offered to receive a single dose of Ad26.COV2.S, under the conditions delineated in Section 6.4. Participants from the Ad26.COV2.S arm enrolled during the double blinded phase, will continue in the same arm to receive their second dose, if applicable (refer to Section 6.4).

*Upon implementation of Protocol Amendment 6, all ongoing participants in the study who received only a single vaccination with Ad26.COV2.S in the study will be offered a single booster dose of Ad26.COV2.S vaccine under the conditions delineated in Section 6.5. Participants who already received 2 vaccinations with Ad26.COV2.S at the 5×10^{10} vp dose level or any COVID 19 vaccinations outside of the study (including the Janssen vaccine) at the time of local approval of Protocol Amendment 6 are not eligible to receive a booster vaccination with Ad26.COV2.S.

1.3. Schedules of Activities

As of Amendment 7, the number of on-site visits for participants who are not part of the Immunogenicity Subset is reduced. For these participants, any outstanding on-site visits will be replaced by phone call visits. Also, active follow-up of suspected COVID-19 episodes for all participants is replaced by a passive follow-up approach.

All participants will be reconsented either at the upcoming study Visit 7 or at an unscheduled visit (whichever comes first) and may be performed on-site or by phone call as per local informed consent process guidelines. Reconsenting at the study site should be performed as soon as operationally feasible and preferably within 4 weeks after site approval of Amendment 7. The eCOA stop will be done at the study site level based on approval of Amendment 7.

No further booster doses will be administered under Protocol Amendment 7, except if there is a medical reason that prevented a participant to receive the Ad26.COV2.S vaccine prior to acceptance of Protocol Amendment 7 or if there is a non-availability of other vaccines to the participant. The investigator should inform participants on the availability of other COVID-19 vaccines.

As of Protocol Amendment 7, visits will be performed by phone call or telemedicine contact, if possible and allowed by local regulations.

1.3.1. Non-immunogenicity Subset (As of Amendment 7)

Phase	Study Period		Long-term Follow-up Phone calls		
Visit Number ^a	7 ^b	8 ^b	9	10	Exit ^c
Visit Timing	Visit 4 + 24 w	Visit 4 +52 w	Visit 4 +78 w	Visit 4 +104 w	
Visit Day/Week	Week 32* (6m post Day 57)	Week 60* (1y post Day 57)	Week 86* (18m post Day 57)	Week 112* (2y post Day 57)	
Visit Window	-106 to +28 days	±21 d	±28 d	±28 d	
Informed consent for Protocol Amendment 7 ^d	● ^b	● ^b			
MAAE recording ^e			Continuous		●
(S)AE recording ^f			Continuous		●
Passive follow up of COVID 19 ^g			Continuous		●
Concomitant therapies ^h			Continuous		●

* These visits are to be scheduled relative to the planned Day 57 (Visit 4) date. The last study visit can occur for some participants at an earlier timepoint (out of the window), eg, if Visit 4 occurred outside of the protocol-planned window.

a. If allowed by local regulations, study visits may take place at the participant's home or other location in the event of ongoing SARS-CoV-2 transmission in the area of the participant. If possible and allowed per local regulation, visits can be performed by a phone call or a telemedicine contact. Assessments scheduled for the other visits may also be performed by a trained health care professional (HCP), if allowed per local regulations.

- b. Depending on the status of the participants, this visit may be the on-site consenting visit for Protocol Amendment 7 or a phone call visit, if informed consent has already occurred.
- c. For those participants who are unable to continue participation in the study up to Visit 10, but for whom consent is not withdrawn, an early exit visit will be conducted as soon as possible. Participants who wish to withdraw consent from participation in the study will be offered an optional visit for safety follow-up.
- d. Reconsenting may take place either at the next scheduled visit or earlier at an unscheduled visit and may be performed on-site or by phone as per local regulations.
- e. MAAEs are to be reported for all participants from the moment of each vaccination until 6 months after the last vaccination, except for MAAEs leading to study discontinuation which are to be reported during the entire study. New onset of chronic diseases will be collected as part of the MAAEs.
- f. All (S)AEs related to study procedures or non-investigational sponsor products will be reported from the time a signed and dated ICF is obtained until the end of the study/early withdrawal. All other SAEs are to be reported from the moment of vaccination until completion of the participant's last study-related procedure or study contact/phone call. AEs leading to study discontinuation (regardless of the causal relationship) and AESIs are to be reported from the moment of vaccination until completion of the participant's last study-related procedure or study contact/phone call. Suspected AESIs are to be reported from the moment of vaccination until completion of the participant's last study-related procedure or study contact/phone call (see Section 8.3.1). Special reporting situations, whether serious or non-serious, are to be recorded from the time of the last vaccination until 28 days post-vaccination.
- g. From the moment the ICF for Amendment 7 is signed or the stop of the eCOA at the site, the participant moves to the passive follow-up phase schedule. COVID-19 is to be reported as SAE, AE, or MAAE until study end (see Section 8.3.1 for the reporting of COVID-19 events as of Protocol Amendment 7). Ongoing COVID-19 episodes from the date of Amendment 7 approval will not be reported as SAEs, AEs, or MAAEs. Participants may also contact the site at any time in between scheduled visits to report a safety concern (eg, hospitalization) or COVID-19 episodes.
- h. Refer to Section 6.10 for collection and recording of concomitant therapies associated with SAEs, solicited and unsolicited AEs, suspected AESIs, and MAAEs and COVID-19 (S)AEs or COVID-19 MAAEs.

AE = adverse event; AESI = adverse event of special interest; COVID-19 = coronavirus disease-2019; d = day(s); ICF = informed consent form; m = month(s); MAAE = medically-attended adverse event; SAE = serious adverse event; SARS-CoV-2 = severe acute respiratory syndrome coronavirus-2; w = week(s); y = year(s).

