For samples collected prior to implementation of Amendment 7, a serologic test for past or current infection with SARS-CoV-2 may be performed for all participants at Day 1 (before the 1st vaccination) and 14 days (Visit 5), 6 months (Visit 7) and 1 year (Visit 8) after the second vaccination. All participants in the open-label phase will have 1 blood sample taken at the unblinding visit (before open-label vaccination) and at the Booster Vaccination Visit (before booster vaccination), except when the previous blood sampling for the serologic test occurred within 5 days of the visit.^a Samples for the serologic tests will be sent to a central laboratory for testing^b. Participants who test positive will be informed of the result by the study staff.

SAFETY EVALUATIONS

The first 1,000 participants will remain under observation at the study site for at least 30 minutes after each vaccination to monitor for the development of acute reactions. If at the time of the Day 3 safety review of

^a The unblinding visit and the Booster Vaccination Visit may be combined with the scheduled study visit and procedures that would be duplicated should be done only once. If a blood draw is already planned in the scheduled visit, then no additional blood draw is needed.

^b Vaccination with Ad26.COVID-19 may interfere with some serologic assays utilized at local community health clinics/commercial laboratories, by seeking and identifying the spike protein in the vaccine and rendering a false positive result. For this reason, participants will be encouraged to not seek testing outside the study. If a participant requires testing outside of the protocol-mandated testing schedule, the site will guide them on the appropriate assay that identifies the viral nucleocapsid protein (and not the spike protein).

the initial 1,000 participants no acute reactions have been observed, the observation period at the study site may be reduced to at least 15 minutes, except where local authorities require a longer observation period (eg, Belgium), after each vaccination for the remaining participants in the study.

Solicited and unsolicited AEs collected as part of Safety subset will be collected in the eCRF up to the unblinding visit.

For all participants (throughout the study regardless of any protocol amendment unless specified otherwise):

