- A passive follow-up approach is adopted, defined as follow-up phone call visits by the site instead of on-site study visits to document new COVID-19 events as SAEs, AEs or MAAEs. Participants may also contact the site at any time in between scheduled visits to report a safety concern (eg, hospitalization) or COVID-19 episodes.
- Concomitant medications for these events should be reported.

^a Reference for definition of thrombocytopenia: Updated Proposed Brighton Collaboration process for developing a standard case definition for study of new clinical syndrome X, as applied to Thrombosis with Thrombocytopenia Syndrome (TTS). 18 May 2021. <https://brightoncollaboration.us/wp-content/uploads/2021/05/TTS-Interim-Case-Definition-v10.16.3-May-23-2021.pdf>. Accessed: 02 September 2021.

- If a COVID-19 confirmatory laboratory or assay read-out is available, this should be reported in the eCRF (self-reported or as part of CIOMS form). The method of the laboratory or assay read-out should be documented.

For participants in the Safety Subset (applicable to double-blind phase only):

- Solicited AEs, collected through an e-Diary, will be recorded from the time of each vaccination until 7 days post-vaccination. If these solicited signs and symptoms are not resolved by that time, the participant will continue to complete the e-Diary until Day 29 post-vaccination or until they are resolved, whichever comes first.
- All other unsolicited AEs, whether serious or non-serious, will be recorded from the time of each vaccination until 28 days post-vaccination. Unsolicited AEs with the onset date outside the timeframe defined above (>28 days after previous study vaccination), which are ongoing on the day of the subsequent vaccination, should be recorded as such.

After the unblinding visit, participants in the Safety Subset will stop the collection of solicited AEs and will not continue in the Safety Subset for any subsequent vaccination. Newly enrolled participants in the open-label phase will not participate in the Safety subset.

STATISTICAL METHODS

Sample Size Calculation

Efficacy (Total Sample Size)

For the double-blind phase, the sample size is determined using the following assumptions:

- a VE for molecularly confirmed, moderate to severe/critical SARS-CoV-2 infection of 65%.
- type 1 error rate $\alpha = 2.5\%$ to evaluate VE of the vaccine regimen
- a randomization ratio of 1:1 for active versus placebo.

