1.3.6. Participants With (Suspected) COVID-19

1.3.6.1. Passive Follow-up (As of Amendment 7)

As of Amendment 7, active follow-up of suspected COVID-19 episodes will be replaced by a passive follow-up approach.

New suspected COVID-19 episodes will be participant-reported and may include available laboratory findings from local testing. Site staff will collect information on the new COVID-19 episodes at scheduled time points and report these as SAEs, AEs, or MAAEs, as applicable. Participants may also contact the site at any time in between scheduled visits to report a safety concern (eg, hospitalization) or COVID-19 episodes. Concomitant therapies related to these events are to be reported, as well as any confirmatory COVID-19 laboratory information, if available. As of Protocol Amendment 7, there will be no further central testing for COVID-19 events.

Guidance on (S)AE coding may be provided.

Some participants will have an ongoing COVID-19 episode at time of signing the informed consent of Protocol Amendment 7. Also, under Protocol Amendment 7, the eCOA will be decommissioned. Hence, participants with an ongoing COVID-19 episode will stop using the eCOA as of site approval of Amendment 7. The outstanding activities planned for the follow-up of COVID-19 episodes will also end on that date for the participants (eg, no further samples, no MRU completion, no MA-COV completion, no further visit in the context of the COVID-19 follow-up). The eCOA will be stopped based on approval of Protocol Amendment 7 at each study site.

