Following EUA approval, Ad26.COV2.S EUA, conditional licensure, or approval in any country of COVID-19 vaccines, all participants were gradually unblinded and a single dose of Ad26.COV2.S was offered to enrolled participants who initially received placebo. Also, the epidemic continued, and new variants of concern emerged, national recommendations introduced booster vaccination. The primary analysis of the study that described the double-blind phase has been completed and the primary objective has been met. Further efficacy evaluations of the open-label data have limitations, due to the unblinding and the loss of the placebo group, due to the loss of randomization, as many participants in the placebo groups in the studies did not cross over to Ad26.COV2.S (eg, because they received another vaccine), and the participants' knowledge of the number of doses received or the timing since vaccination, which could have led to behavioral changes impacting the results. Operational challenges have impacted the feasibility of a strict follow-up of any COVID-19 episode and active surveillance cannot be sustained. Because of these reasons, the protocol has been amended to reduce the need for on-site visits and to change the requirements for COVID-19 episode reporting by applying a passive surveillance approach. Participants in the Immunogenicity Subset will continue with the on-site study visits. There are no changes to follow-up of safety endpoints, including the reporting of adverse events of special interest (AESIs). Two analyses are planned for the study: a first analysis will be conducted for the open-label phase of the study (using the initially designed "active" follow-up of COVID-19 events) and a second end-of-study analysis is planned (using passive follow-up of COVID-19 events).

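### Footnote g of both Amendment 7 schedules can be read as barring SAE reporting of a later hospitalisation or death in a COVID-19 episode open at the switch, contrary to the protocol's other safety rules

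*Protocol*

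**What the plan says.** Two provisions govern an episode that is open when a site moves to Amendment 7.

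- **Active route.** Section 1.3.6.1 says that "participants with an ongoing COVID-19 episode will stop using the eCOA as of site approval of Amendment 7". It adds: "The outstanding activities planned for the follow-up of COVID-19 episodes will also end on that date for the participants". Its examples are samples, the MRU and MA-COV forms, and COVID-19 visits.
- **Safety-reporting route.** Footnote g of Sections 1.3.1 and 1.3.2 says: "Ongoing COVID-19 episodes from the date of Amendment 7 approval will not be reported as SAEs, AEs, or MAAEs". The Synopsis (Safety Evaluations) describes the replacement calls as serving "to document new COVID-19 events as SAEs, AEs or MAAEs", so they are aimed at new events.

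Other current text points the other way.

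- Footnote f, directly above footnote g, has no COVID-19 exception: "All other SAEs are to be reported from the moment of vaccination until completion of the participant's last study-related procedure or study contact/phone call".
- The Synopsis (Safety Evaluations) requires all SAEs whatever their cause, under the heading "For all participants (throughout the study regardless of any protocol amendment unless specified otherwise".
- Section 2.1 states: "There are no changes to follow-up of safety endpoints, including the reporting of adverse events of special interest (AESIs".
- The Synopsis (Efficacy Evaluations) has COVID-19 hospitalisation and complications, death included, monitored for the whole study. Section 4.1 has all COVID-19 complications entered in the eCRF for the whole study.
- Elsewhere, however, Section 4.1 confines monitoring for complications to the period before Amendment 7.

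**The concern.** A patient who is symptomatic on the switch date can deteriorate days later. The swabs, forms and visits that would have documented this have stopped. If the site follows footnote g to the letter, the hospitalisation or death is not entered as an SAE either.

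Three things are at stake. First, SAEs during the entire study are a secondary safety endpoint, and it is carried into both open-label phases. Second, the open-label active-phase endpoints (severe/critical disease, medical intervention, COVID-19 death) may lose outcomes that occur after observation ends. Third, the passive-phase COVID-19 endpoints consist entirely of SAEs, AEs and MAAEs, so an outcome kept out of AE reporting cannot appear there.

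**Working it through.** The protocol gives no figure on this point, so the check sets its rules side by side and follows one case: onset before the switch, hospitalisation after it.

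1. **Is the outcome captured by active follow-up?** Not by its instruments. Section 1.3.6.1 ends every outstanding episode activity at site approval.
2. **Is it captured by passive follow-up?** Read literally, no. The calls document new episodes, and footnote g keeps ongoing ones out of SAE, AE and MAAE reporting.
3. **Does the general SAE rule rescue it?** Footnote f says yes without qualification. The Synopsis version applies only unless something else is specified, and footnote g can be taken as such a specification. A site could reasonably act on either text.
4. **Does eCRF capture of complications rescue it?** One statement in Section 4.1 says capture runs for the whole study. Another limits complication monitoring to the period before Amendment 7. The first also sits beside the withdrawal of the MA-COV and MRU forms, and the text available names no replacement form.
5. **Does adjudication rescue it?** The Synopsis (Case Definitions) allows readjudication when new information arrives, and the last decision governs. After Amendment 7 the committee may work from passive follow-up data such as COVID-19 AE/SAE data, CIOMS forms and local laboratory results. If footnote g withholds the SAE, the main input is missing.
6. **When is the switch?** Three anchors are used:
   - Footnote g uses Amendment 7 approval for the reporting bar.
   - Section 1.3.6.1 speaks of episodes ongoing at consent signing, then stops the eCOA at site approval.
   - The phase definition (Synopsis 2.2 and Section 3, 2.2) uses consent or eCOA stop, whichever is first.

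   Section 1.3 asks for reconsent preferably within 4 weeks of site approval. An episode that starts between approval and consent is therefore new under one anchor and ongoing under another.

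**Size.** The protocol does not give the number of episodes open at the switch. Any figure needs assumptions: open episodes = participants × incidence per month × months an episode stays open.

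- Assumed 20,000 participants, 1% per month, 0.5 month: 20,000 × 0.01 × 0.5 = 100.
- Assumed 30,000 participants, 3% per month, 1 month: 30,000 × 0.03 × 1 = 900.
- With the protocol's only incidence assumption (1% to 4% per year, moderate to severe/critical disease at study start) and the same participants and durations: 20,000 × 0.01/12 × 0.5 ≈ 8, and 30,000 × 0.04/12 × 1 = 100.

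The result runs from about 8 to 900. It counts open episodes, not hospitalisations or deaths that would be missed, so it does not measure the loss.

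**The case against.** The strongest reply is that footnote g speaks of episodes, not of their later serious outcomes. An ongoing episode is already in the database as an active-phase COVID-19 episode, and entering it again as an AE would count it twice. On that reading the sentence is a sensible guard. It fits the assignment of passive reporting to new episodes, and the statement that safety follow-up is unchanged. The next sentence of footnote g even invites participants to report a hospitalisation at any time. The COVID-19 endpoints concerned are exploratory and descriptive, and the primary analysis is complete.

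Much of this stands. The benign reading may well be the intended one, and it is a reason not to delete the sentence outright. The exploratory status also limits the efficacy consequence, though not the consequence for the secondary SAE endpoint. What the reply does not cure is the wording. The footnote does not say it concerns duplicate entry, it names SAEs explicitly, and it appears in the schedules that sites work from.

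A reader might infer that post-switch hospitalisations and deaths have nowhere to be recorded. The documents do not support that. The general SAE rule, the study-long eCRF capture in Section 4.1 and the study-long monitoring in the Synopsis all remain in force on their face. Footnote g also refers to Section 8.3.1 for COVID-19 reporting, and the table of contents lists Section 8.3.6 on disease-related events that do not qualify as AEs or SAEs. The text of neither was available here, and either could settle the question. Nor do the documents show that the loss would differ by site, calendar time or cohort. Site-by-site switching makes that possible, no more.

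**Conclusion.** The point holds as a contradiction with a real reporting risk. One instruction, present in both Amendment 7 schedules, can be read as forbidding SAE reports that footnote f and the Synopsis require, for episodes whose active follow-up stops at the same switch. A hospitalisation or death in such an episode may go unreported as an SAE and may be missed by both sets of open-label COVID-19 endpoints. Whether that happens depends on how a site reads footnote g and on what Sections 8.3.1 and 8.3.6 say. The number of outcomes affected cannot be derived from the documents. Only episodes that worsen after the switch are exposed for severity and death; symptom duration stops being observed for every open episode. Because a secondary safety endpoint is involved and the correction is small, it should be made.

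**What to change.** - **Footnote g, Sections 1.3.1 and 1.3.2.** Keep the sentence but limit it to preventing a second entry of an episode already recorded in the active phase. State that it does not override SAE reporting: any later event in that episode that meets seriousness criteria is reported as an SAE, linked to the episode and made available to the Clinical Severity Adjudication Committee.
- **Phase.** State whether such an event counts in the active or the passive phase.
- **Cut-off.** Use one date in footnote g, Section 1.3.6.1 and the phase definitions in the Synopsis and Section 3.
- **Section 4.1.** Reconcile the statement limiting complication monitoring to the period before Amendment 7 with the statement on study-long eCRF capture, and with the Synopsis (Efficacy Evaluations). Check that Sections 8.3.1 and 8.3.6 agree.
- **Sites.** At the first phone call, ask once about the outcome of any episode open at the switch.

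The cost is two footnotes, alignment of a few sentences, and one question per affected participant. No new visit or sample is needed.
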